2.3 EXPLORATORY OBJECTIVES

- To assess the impact of providing DNA-based dietary guidelines via the DnaNudge App, on improving glucose regulation in pre-diabetic individuals
- To assess the impact of providing DNA-based dietary guidelines via the DnaNudge App, on the secondary outcomes outlined in section 2.2.
- To explore the utility of an app as a delivery mechanism for DNA-based dietary advice.
- To examine the changes in leptin measurements via saliva samples during the study.

3 STUDY DESIGN

3.1 TYPE OF STUDY

Physiological; pilot study; RCT, parallel design with an active control.

3.2 DURATION

23 months.

3.3 STUDY POPULATION

Adults with impaired glucose regulation defined by HbA1c, impaired fasting glucose (IFG) or impaired glucose tolerance (IGT) in line with WHO criteria (N = 180):

HbA1c:

- < 42 mmol/mol (6.0%): Non-diabetic
- 42 < 47 mmol/mol (6.0–6.4%): IGT – Pre-diabetic
- ³ 48 mmol/mol (6.5%): Type 2 diabetic

| IFG (World Health Organization 2006):

- Fasting plasma glucose: 6.1mmol/L (110mg/dL) ≤ IFG ≤ 6.9mmol/L (125mg/dL)
- 2 hr plasma glucose: < 7.8 mmol/L (140mg/dL)

IGT (World Health Organization 2006):

- Fasting plasma glucose: < 7mmol/L (126mg/dL)
- 2 hour plasma glucose: 7.8mmol/L (140mg/dL) ≤ IGT < 11mmol/L (200mg/dL)

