4 PARTICIPANT ENTRY

4.1 PRE-REGISTRATION EVALUATIONS

Potential participants will undergo a screening process prior to entry into the study. Potential participants will be invited to the clinical research facility where they will be talked through the consent procedure and allowed to ask any questions they may have. Following consent and verification that they are eligible via the inclusion and exclusion criteria, they will undergo a glucose regulation test via finger prick blood sample that will be analysed either via a point of care (POC) HbA1c test, or a lab analyser, to measure HbA1c. The lab analyser (TOSOH G8 analyser) will be used to assess HbA1c on a capillary sample if the Siemens DCA Vantage Analyser POC device is unavailable or returns values that are out of the acceptable range for accuracy. Both devices will be used in line with manufacturer instructions. If a participant is found to be type 2 diabetic they will be referred to their GP for further care.

The HbA1c test results will be interpreted according to WHO criteria:

- HbA1c below 42 mmol/mol (6.0%): Non-diabetic
- HbA1c between 42 and 47 mmol/mol (6.0–6.4%): IGT – Pre-diabetic
- HbA1c of 48 mmol/mol (6.5%) or over: Type 2 diabetic

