9.4 ANALYSIS OF PRIMARY AND SECONDARY OUTCOME MEASURES

Data will be analysed after all primary and secondary outcomes have been recorded for the last participant. The primary analysis will be conducted under the ITT principle using modified analysis of covariance (ANCOVA) (Yang & Tsiatis 2001). Raw and adjusted mean differences in PFG at week 6 between the intervention and control arm will be presented with 95% confidence interval (95%CI). The adjusted mean difference will be estimated using a linear regression model of week 6 FPG to baseline PFG and treatment arm adjusted for age and sex. An interaction of baseline FPG with the indicator for treatment arm will be included. PFG will be log transformed and variables will be centred.

The primary null hypothesis is no difference in W6 FPG between the intervention and the control arm. It will be rejected if the adjusted 95%CI of the mean difference does not include 0. The robustness of the results will be tested using PP analysis and two alternative models (repeated measure mixed model and non parametric model). Missing data will be imputed using the multiple imputation with chain equation (MICE) method if there is no evidence against the assumption of data missing at random.

The secondary analysis will be conducted under the ITT principle. The ANCOVA will be used to compare mean difference in FPG, weight, BMI, mass, waist, fasting lipids and blood pressure at the different time points (W6, W12 and W26). In addition, mixed models will be used to compare the overall changes in these outcomes over the all follow up period. Adequacy of the models will be assessed through residual plots and Shapiro-Wilk tests for normality. Non-parametric methods may be used in case of severe departure from normality. In the addition, logistic regression model will be used to compare the proportion of participants with IGR between the two arms. Change in dietary habits will be analysed using polytomous regression.

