## Definitions

Impaired glucose regulation: impaired fasting glucose (IFG) or impaired glucose tolerance (IGT).

Impaired fasting glucose:

$6.1\text{ mmol/L} \leq \text{Fasting plasma glucose (FPG)} \leq 6.9\text{ mmol/L}$  AND  $2\text{ hr plasma glucose: } < 7.8\text{ mmol/L}$

Impaired glucose tolerance:

- $\text{FPG} \geq 7\text{ mmol/L}$  AND  $7.8\text{ mmol/L} \leq \text{2-hour plasma glucose} < 11\text{ mmol/L}$  after glucose load
- HbA1c between 42 and 47 mmol/mol (6.0–6.4%)

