#### - Per protocol population

In addition, the primary endpoint will be analysed with the Per Protocol population (PPP), which consists of those subjects in the ITT population who complete the study with no significant deviations from the planned protocol procedures. The exclusion will be as follows:

- Participants without impaired glucose regulation before inclusion [see definition page 6]
- Significant protocol deviation such as non respect of inclusion / exclusion criteria
- Pregnancy during follow-up
- Participants loss to follow-up or who withdrew consent

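### Protocol 3.3 prints the IGT 2-hour upper limit as 11 mmol/L and as 200 mg/dL, which differ by about 0.1 mmol/L, and the SAP carries only the 11

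*Protocol*

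**What the plan says.** Protocol 3.3 defines the glucose categories in both units. Impaired fasting glucose (IFG) is "6.1mmol/L (110mg/dL) ≤ IFG ≤ 6.9mmol/L (125mg/dL"), with a 2-hour value below 7.8 mmol/L. IGT needs "Fasting plasma glucose: < 7mmol/L (126mg/dL") together with a 2-hour value that starts at "2 hour plasma glucose: 7.8mmol/L (140mg/dL") and ends at "IGT < 11mmol/L (200mg/dL").

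SAP Definitions restates the 2-hour limit in mmol/L only: "2-hour plasma glucose} < 11" (the brace is left over from equation markup). Neither document prints another 2-hour upper limit or says which unit governs.

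The definition is used in three places:

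- **Analysis.** Protocol 9.4 plans a logistic regression to "compare the proportion of participants with IGR between the two arms".
- **Per-protocol set.** SAP 1.6 excludes "Participants without impaired glucose regulation before inclusion" and refers back to the definition.
- **Eligibility.** Protocol 4.2 names OGTT as one of the permitted routes to impaired glucose regulation.

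**The concern.** The two figures are printed as one limit but are different values. A 2-hour result between them is inside the study's disease definition by mg/dL and outside it by mmol/L. The SAP drops the mg/dL figure, so whoever programs the IGR indicator will probably code 11.0 literally, and nothing in the SAP would show that the protocol also gives a slightly higher limit.

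No other glucose category picks these results up. IFG requires a 2-hour value below 7.8 mmol/L, and the documents print no 2-hour limit for diabetes. Read by the mmol/L figure, such a result is neither IFG nor IGT. In a yes/no IGR variable based on glucose it would be coded like a normalised result, although it lies at the top of the range. HbA1c is not measured at week 6 (Protocol 3.5), so IGR status at that visit can rest only on glucose.

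**Working it through.** **Inputs.** Six glucose pairs are printed in both units: five in Protocol 3.3 and one (5.6 mmol/L, 100 mg/dL) in Protocol 1.1. The conversion factor is not stated, so I derive it from the five pairs not in question.

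**Step 1: the factor.** If the mmol/L figure m is rounded to one decimal, a pair (m, g) is consistent with any factor from g/(m + 0.05) to g/(m − 0.05).

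| mmol/L | mg/dL | g/m | Factors allowed | g/18.0 |
|---|---|---|---|---|
| 5.6 | 100 | 17.86 | 17.70 to 18.02 | 5.56 |
| 6.1 | 110 | 18.03 | 17.89 to 18.18 | 6.11 |
| 6.9 | 125 | 18.12 | 17.99 to 18.25 | 6.94 |
| 7 | 126 | 18.00 | 17.87 to 18.13 | 7.00 |
| 7.8 | 140 | 17.95 | 17.83 to 18.07 | 7.78 |
| **11** | **200** | **18.18** | **18.10 to 18.26** | **11.11** |

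The first five intervals overlap in 17.99 to 18.02, and all five pairs reproduce to one decimal at 18.0. The sixth needs at least 18.10, so it does not fit.

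**Step 2: the gap.** With factors 17.99 to 18.02:

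- 200 mg/dL = 200/18.02 to 200/17.99 = 11.10 to 11.12 mmol/L.
- 11 mmol/L = 11 × 17.99 to 11 × 18.02 = 197.8 to 198.2 mg/dL after rounding, working from the unrounded factors.

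The two limits are about 0.1 mmol/L, or 2 mg/dL, apart. If the mg/dL figures are also treated as rounded, 200 mg/dL is 11.04 to 11.16 mmol/L, still above 11.0.

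**Step 3: classification**, at factor 18.016 and with the protocol's fasting criterion met:

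| 2-hour, mmol/L | mg/dL | Below 11 mmol/L? | Below 200 mg/dL? |
|---|---|---|---|
| 10.9 | 196.4 | yes | yes |
| 11.0 | 198.2 | no | yes |
| 11.05 | 199.1 | no | yes |
| 11.09 | 199.8 | no | yes |
| 11.2 | 201.8 | no | no |

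**Step 4: how many results.** The documents give no distribution for 2-hour glucose. I assume it is normal with mean 7, 8 or 9 and SD 1.5, 2 or 2.5 mmol/L, and compute P = Φ((11.1 − mean)/SD) − Φ((11.0 − mean)/SD).

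- Smallest: mean 7, SD 1.5. P = Φ(2.733) − Φ(2.667) = 0.0007.
- Largest: mean 9, SD 2. P = Φ(1.05) − Φ(1.00) = 0.0118.

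Protocol 9.4 compares two arms of 60, with OGTTs at weeks 6, 12 and 26: 2 × 60 × 3 = 360 follow-up tests if nobody is lost. The expected number in the gap is 360 × 0.0007 = 0.25 to 360 × 0.0118 = 4.2, or about 0 to 4. At week 6 alone (120 tests) it is 120 × 0.0007 = 0.08 to 120 × 0.0118 = 1.4.

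**The case against.** Much can be said for leaving this alone.

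**The 11 is just a rounded figure.** The same section prints 7 mmol/L without a decimal, and 11 does match 200 mg/dL to the nearest whole number. But the 7 is exact to one decimal (126/18 = 7.00), whereas 200/18 is 11.1. The rounding would be harmless beside the mg/dL figure; in the SAP the 11 stands alone as a cut-off.

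**The trial works in mmol/L.** The SAP's baseline table records glucose in that unit, so in practice one limit would be applied consistently. This stands, and it means the arms would be treated alike. It does not settle which of the protocol's two limits was intended.

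**The affected analysis is thin.** The IGR comparison appears in Protocol 9.4 but not among the SAP's secondary endpoints, and SAP 1.15 gives 2-hour glucose no analysis beyond ANCOVA and the mixed model. This stands and limits the weight of the point.

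**The fasting criterion comes first.** As printed, SAP Definitions requires fasting glucose at or above 7 mmol/L for glucose-defined IGT, where the protocol requires it below 7. Under the SAP wording, a participant fasting below 7 is not IGT by glucose at any 2-hour value, so the upper limit decides nothing for them. This stands: it is the larger conflict in that definition, and changing the 11 alone would leave it in place.

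A reader might also infer that the discrepancy removes people from the trial or from the per-protocol set. The documents give little support for that. The only glucose-regulation test at screening is HbA1c (Protocol 4.1 and 6.2.1), where "HbA1c between 42 and 47 mmol/mol" counts as pre-diabetic, and the SAP lists that band as a separate item under IGT. Assignment follows Visit 2, while the first scheduled OGTT is at Visit 3. What remains is someone admitted on an outside OGTT with a non-qualifying HbA1c, or a query when criteria are verified again at Visit 3.

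A reader might likewise take the HbA1c band in 3.3, which appears as 42 < 47, for a second inconsistency. A neighbouring line has a garbled symbol before 48, so this is probably a text-extraction fault, and Protocol 4.1 and the SAP agree with each other.

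**Conclusion.** The point holds, as a minor one. The protocol's two figures for the IGT upper limit are not the same value, and the SAP has carried forward one of them. The gap is about 0.1 mmol/L.

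The practical effect is about 0 to 4 of some 360 follow-up OGTTs in the two-arm IGR comparison. That range rests on the assumed normal distributions. It is more likely too high than too low: it supposes no losses and that the fasting criterion is met every time, and at weeks 12 and 26 an HbA1c of 42-47 mmol/mol would count as IGR whatever the 2-hour value. The upper end (mean 9, SD 2) also puts about 16% of results above 11 mmol/L, which is a lot for a trial that excludes diabetes.

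Effects on eligibility and the per-protocol set are close to nil. The primary analysis, continuous week-6 fasting glucose by intention to treat, does not use this limit, and neither does the sample size.

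**What to change.** - In Protocol 3.3, reconcile the mmol/L and mg/dL figures for the IGT 2-hour upper limit so that both express one value. The investigators should decide which was intended.
- Carry that value into SAP Definitions in mmol/L to one decimal place, so that the programmed cut-off cannot differ from the protocol.
- In the same SAP edit, reconcile the IGT fasting criterion with the protocol's. Without this, the glucose definition of IGT in the two documents still disagrees, and by more than the 2-hour limit does.

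The cost is one figure in the protocol and two entries in one SAP definition. No visit, assay or sample size changes. The edits should be made before any IGR indicator is derived.

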3.4 DESCRIPTION OF STUDY DESIGN

Following informed consent, study participants will undergo baseline assessment including assessment of anthropometry, glucose tolerance, metabolism and diet. A trial commencement questionnaire (see Appendix 2) will be completed by each participant upon entry into the trial, and a trial completion questionnaire (see Appendix 4) will be given after 12 weeks of the intervention and after the 26-week follow-up measurement. The questionnaires will address lifestyle factors that may impact the outcomes of the study, and data regarding DnaNudge App utility. DNA will be sampled from saliva from all participants. Two saliva samples will be taken at the baseline assessment (Visit 3 – see [Table 1](#)). One sample will be used to create the DNA-based dietary recommendations and the second sample will be used to assess the leptin levels of the participants. Leptin will be measured from saliva samples taken at the 6-, 12-, and 26-week clinical visits to assess the changes in the hunger hormone during the study. Participants will be

assigned to one of three cohorts using stratified blocked randomisation by age and gender (block size = 15):

1. Control arm (n = 60):

- Participants will receive general health guidelines according to the NICE guidelines, as per standard care.
- Active control

2. Intervention arm (n = 60):

- Participants will receive DNA-based health guidelines via a genetic report (see Appendix 13).

3. Exploratory arm (n = 60):

- Participants will receive DNA-based health guidelines via the DnaNudge App.

The DNA for all arms of the study will be analysed for pre-determined single nucleotide polymorphisms (SNPs) relevant to metabolism. Participants in the intervention arm, will be provided with a hard-copy of a genetic report (for an example report see Appendix 13), which will explain how their SNPs influence their dietary habits. Participants in the exploratory arm, will be given personalised DNA-based dietary advice via the DnaNudge App. Participants in the control arm will be provided with a summary of NICE guidance via a dietitian, as per standard care.

Participants will then be reviewed after 6 and 12 weeks with repeat baseline measures. Participants in the control arm will be offered a personalised nutrition plan on completion of the study. Participants will be asked to complete a food frequency questionnaire (see Appendix 12) before their initial consultation with the dietitian (Visit 4 – see [Table 1](#)), and at the 6-, 12- and 26-week follow up clinical visits. Participants will also be asked to perform a 24-hour recall at each follow-up phone call with a dietitian (Visits 5, 7, 9 & 11 – see [Table 1](#)). A summary of the activities for each participant is given in [Table 1](#). Data from the App will also be used in exploratory analysis to examine usage patterns and decision making as a result of the DNA-based dietary recommendations.

See [Figure 1](#) for a diagram of the study design and estimated timeframe.

3.5 STUDY OUTCOME MEASURES

Primary outcome: Difference in 0 minutes glucose on 75g oral glucose tolerance test between the control arm and intervention arm at 6 weeks

Secondary outcomes: 120 minutes glucose on 75g oral glucose tolerance test
0 minutes glucose on 75g oral glucose tolerance test
HbA1c
Weight
BMI
Lean mass
Fat mass
Waist circumference
Total cholesterol
Fasting Triglycerides
LDL cholesterol
HDL cholesterol
HOMA Insulin sensitivity and secretion measurement
120 minute c-peptide following 75g oral glucose tolerance test
Systolic blood pressure
Diastolic blood pressure
Food frequency (by food frequency questionnaire and interviews) Energy intake
Carbohydrate intake
Fat intake
Saturated fat intake
Salt intake
Vitamin D
Vitamin B6
Vitamin B12

All secondary outcomes will be measured at 6, 12 and 26 weeks (with the exception of HbA1c which will only be measured at 12 and 26 weeks).

4 PARTICIPANT ENTRY

4.1 PRE-REGISTRATION EVALUATIONS

Potential participants will undergo a screening process prior to entry into the study. Potential participants will be invited to the clinical research facility where they will be talked through the consent procedure and allowed to ask any questions they may have. Following consent and verification that they are eligible via the inclusion and exclusion criteria, they will undergo a glucose regulation test via finger prick blood sample that will be analysed either via a point of care (POC) HbA1c test, or a lab analyser, to measure HbA1c. The lab analyser (TOSOH G8 analyser) will be used to assess HbA1c on a capillary sample if the Siemens DCA Vantage Analyser POC device is unavailable or returns values that are out of the acceptable range for accuracy. Both devices will be used in line with manufacturer instructions. If a participant is found to be type 2 diabetic they will be referred to their GP for further care.

The HbA1c test results will be interpreted according to WHO criteria:

- HbA1c below 42 mmol/mol (6.0%): Non-diabetic
- HbA1c between 42 and 47 mmol/mol (6.0–6.4%): IGT – Pre-diabetic
- HbA1c of 48 mmol/mol (6.5%) or over: Type 2 diabetic

4.2 INCLUSION CRITERIA

In order to be eligible to participate in this study, an individual must meet all of the following criteria:

- Provision of signed and dated informed consent form
- Adults over 18 years of age
- Impaired glucose regulation including IFG and IGT by fasting glucose, OGTT or HbA1c criteria
- Access to smartphone with an operating system of iOS 8.0 or above, or Android 4.0 or above.

4.3 EXCLUSION CRITERIA

An individual who meets any of the following criteria will be excluded from participation in this study:

- Diabetic
- Pregnant or planning pregnancy
- Breastfeeding
- Enrolled in other clinical trials
- Have active malignancy or under investigation for malignancy
- Severe visual impairment
- Reduced manual dexterity

- Use of psychiatric, anti-diabetic, and/or weight loss medication, and/or oral steroids
- Bariatric surgery
- History of illnesses that could interfere with the interpretation of the study results (e.g. HIV, Cushing syndrome, chronic kidney disease, chronic liver disease, hyperthyroidism, hereditary fructose intolerance, alcohol or substance abuse)
- Unable to participate due to other factors, as assessed by the Chief Investigator

4.4 STRATEGIES FOR RECRUITMENT AND RETENTION

Participants will be recruited through some/all of the following approaches:

1. Communication with Waitrose customers and their partners through Waitrose customer/partner communication platforms
2. Imperial College Healthcare Trust Diabetes Clinics
3. Healthy volunteer database in the Imperial Clinical Research Facility
4. NIHR CRN distribution of text messages to individuals chosen by the NIHR CRN based on study inclusion/exclusion criteria in London Clinical Commissioning Groups (CCGs).
5. Flyers for display in hospitals/Imperial Clinical Research Facility (ICRF), Imperial College London/Community Centre noticeboards.
6. Advertisement in local London newspapers with same information as flyer.
7. The use of Patient Identification Centres (PICs) to identify and contact potential participants through one of the aforementioned approved methods e.g. text messages
8. Advertisement of the study via Diabetes UK through for example, their website, social media.
9. Opportunistic recruitment via either GP staff, Clinic staff, or Trial Team staff providing patients with study information before/during/after their consultation.

If identified through method (1), (3), (5) and (6), the initial information that will be communicated will direct the potential participants to self-assess if they may be pre-diabetic by completing the Leicester Risk Score Assessment (Gray et al. 2010), available on the Diabetes UK website (<https://riskscore.diabetes.org.uk/start>). Participants will be offered the opportunity to contact the clinical trial team if they would like to partake in the trial. The clinical trial team will then invite the potential participant to the Clinical Research Facility for a screening appointment. If identified through method (2), (5), (7) and (9), the participants will be identified from the current registry of prediabetic individuals who were identified through standard care. They will be provided with contact details for the study should they wish to participate. If identified through method (8), participants will be directed to the clinical trial website and/or the Trial Team contact email address and phone number if they would like to find out more information about the trial. Of note, patients can only be approached by members of the Trial Team if they have

given permission via their direct care team. If the potential participant is considered eligible by any of the above methods, they will be contacted via email or telephone by the clinical trial team to ask them if they would like to undergo a screening test at the clinical research facility to assess their suitability for the trial.

Given the high rate of diagnosis of diabetes and pre-diabetic individuals by the North-West London GP network in 2016, we anticipate the accrual rate for N = 180 pre-diabetic individuals to fulfil our planned recruitment schedule of N = 60 participants every 3 months.

4.5 WITHDRAWAL CRITERIA

Each participant has the right to withdraw from the study at any time. In addition, the Investigator may discontinue the participation of a participant from the study at any time, if the Investigator considers it necessary for any reason including:

- Pregnancy
- Ineligibility
- Significant protocol deviation
- Significant non-compliance with treatment regimen or study requirements
- Withdrawal of consent
- Loss to follow-up

Following participant withdrawal, no further clinical tests will be performed, and no further information will be obtained from the participant's DnaNudge App for the purposes of the trial. All data recorded prior to withdrawal may be analysed in the context of determining reasons for withdrawal. Participants will have the option of participating in a follow-up interview to ensure patient well-being and to provide reasons for withdrawal if they wish. The reason for withdrawal will be recorded in the CRF. Participants will not be required to provide reasons for withdrawing from the study. Participant withdrawal will result in exclusion from the study if the length of time prior to withdrawal is not sufficient to provide useful data for the study.

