6.2.4 EARLY TERMINATION VISIT

In the case of early termination, an interview will be conducted with the participant to determine reasons for termination if appropriate, and/or to determine if the data collected thus far may be useful.

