9 STATISTICS AND DATA ANALYSIS

9.1 ANALYSIS DATASETS

Primary analyses will be conducted following the intention to treat (ITT) principle. All participants who are randomised into the study will be included in the ITT analysis. Such participants constitute the Full Analysis Set (FAS) for this study. In addition, the primary endpoint and the main secondary outcomes will also be analysed with the Per Protocol Analysis Set (PPS), which will consist of those subjects in the FAS who complete the study with no significant deviations from the planned protocol procedures.

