10.2 CONSENT

Consent to enter the study must be sought from each participant only after a full explanation has been given, an information leaflet offered and time allowed for consideration. Signed participant consent should be obtained. The right of the participant to refuse to participate without giving reasons must be respected. After the participant has entered the study the clinician remains free to give alternative treatment to that specified in the protocol at any stage if he/she feels it is in the participant's best interest, but the reasons for doing so should be recorded. In these cases the participants remain within the study for the purposes of follow-up and data analysis. All participants are free to withdraw at any time from the protocol treatment without giving reasons and without prejudicing further treatment.

Please see Appendix 5 for an example consent form.

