11.3 PROTOCOL DEVIATIONS

A protocol deviation is any noncompliance with the clinical trial protocol, or GCP requirements. The noncompliance may be either on the part of the participant, the Investigator, or the study site staff. As a result of deviations, corrective actions are to be developed by the site and implemented promptly.

These practices are consistent with ICH E6:

- 4.5 Compliance with Protocol, sections 4.5.1, 4.5.2, and 4.5.3
- 5.1 Quality Assurance and Quality Control, section 5.1.1
- 5.20 Noncompliance, sections 5.20.1, and 5.20.2.

It is the responsibility of the site to use continuous vigilance to identify and report deviations within 7 working days of identification of the protocol deviation, or within 7 working days of the scheduled protocol-required activity. All deviations must be addressed in study source documents, reported to the Trial Manager and the study Sponsor. Protocol deviations must be sent to the local IRB as per their guidelines. The site study staff is responsible for knowing and adhering to their IRB requirements.

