## Endpoints

### 1.4 Primary endpoint

The primary endpoint for the ASPIRE trial is the difference in FPG at week 6 between the intervention arm that receives DNA-based diet advice and the control arm. This outcome has been chosen because it is the most sensitive indicator of impaired glucose regulation. Endpoints assessment will not be blind to the study intervention arm allocated.

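### Protocol 4.5 lets an unblinded investigator remove non-compliers and stops their tests, so the week-6 glucose that the ITT analysis needs can be lost selectively

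*Protocol*

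**What the plan says.** Protocol 4.5 puts two ways out of the trial under one heading. Participants may withdraw. Separately, "the Investigator may discontinue the participation of a participant from the study at any time". The grounds listed include significant protocol deviation and "Significant non-compliance with treatment regimen or study requirements", with no threshold for what is significant. The same list also contains withdrawal of consent and loss to follow-up, so the section does not keep the two routes apart. The next paragraph rules: "Following participant withdrawal, no further clinical tests will be performed, and no further information will be obtained from the participant's DnaNudge App". It adds that a withdrawal too early to yield useful data leads to exclusion from the study.

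Protocol 6.2.4 does not fill the gap: "In the case of early termination, an interview will be conducted with the participant to determine reasons for termination if appropriate". No measurement is scheduled there.

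On the analysis side, Protocol 9.1 says "All participants who are randomised into the study will be included in the ITT analysis", and SAP 1.6 agrees. The primary endpoint is fasting plasma glucose (FPG) at Visit 6, Day 42. The protocol summary gives masking as none, and SAP 1.4 says "Endpoints assessment will not be blind to the study intervention arm allocated".

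Two other sections bear on the point. Where a clinician gives alternative treatment, Protocol 10.2 says "In these cases the participants remain within the study for the purposes of follow-up and data analysis". For deviations, Protocol 11.3 says "As a result of deviations, corrective actions are to be developed by the site and implemented promptly".

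**The concern.** An intention-to-treat comparison needs the outcome of every randomised participant, whether or not they followed the advice. Section 4.5 allows measurement to end because of poor adherence, on the judgement of someone who can know the arm. If the diet lowers glucose, those removed from the DNA arm will tend to be those who benefited least. The participants still measured then describe the effect in adherers, not the effect of offering the advice.

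The planned methods do not repair this:

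- **Multiple imputation** (Protocol 9.4, SAP 1.12) is used only if nothing speaks against missing at random. Someone removed before Visit 6 has no post-baseline FPG to inform the imputation.
- **The mixed model** (Protocol 9.4) also relies on missing at random.
- **The non-parametric test** (SAP 1.14) does not address missingness.
- **The per-protocol set** (Protocol 9.1, SAP 1.6) leaves out the same people.

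No planned analysis allows for data missing not at random. Samples not taken cannot be recovered later. A participant removed after Visit 6 keeps the primary endpoint but loses the week-12 or week-26 secondary outcomes.

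**Working it through.** **1. Is there a window before the endpoint?** Yes. Randomisation follows Visit 2 (Protocol 6.2.1), advice starts at Visit 4 (Day 0), and the endpoint is at Visit 6 (Day 42). In between, the Visit 5 call (Day 14) takes a 24-hour dietary recall in the control and intervention arms, so poor adherence can become visible to the trial team.

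**2. Does any other section keep a discontinued non-complier in measurement?** No. Section 10.2 covers only alternative treatment. Section 11.3 asks for corrective action but does not say that visits continue after discontinuation. Section 6.2.4 provides an interview. Section 10.2 does not contradict 4.5, but it does not settle the case either.

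**3. Inputs (SAP 1.14).** Change in FPG is -0.6 mmol/L in the DNA arm and -0.1 in the control arm. Baseline SD is 0.7, post-intervention SD 0.6, correlation 0.4 to 0.6, with 60 per arm. The SAP's own statement of power above 0.9 reproduces. On change scores, the SD is √(0.49 + 0.36 − 2r × 0.42), which is 0.717 at r = 0.4 (power 0.969) and 0.588 at r = 0.6 (power 0.997). The share discontinued before Visit 6, q, is not in the documents. I assume 5% (3 of 60) and 10% (6 of 60).

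**4. Formulas.** Differences are written as reductions, so the true ITT value is 0.6 − 0.1 = 0.5.

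- *DNA arm only.* Assume those removed do no better than control (change -0.1). The retained mean m solves (1−q)m + q(−0.1) = −0.6, so the estimated difference is 0.5/(1−q).
- *Controls only.* Assume removed controls have zero change. The retained control mean is −0.1/(1−q), so the estimate is 0.5 − (0.1/(1−q) − 0.1).
- *Both arms at the same rate.* The estimate is 0.5/(1−q) − (0.1/(1−q) − 0.1).

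| Who is removed | q = 5% | q = 10% |
|---|---|---|
| DNA arm only | 0.526 (+5%) | 0.556 (+11%) |
| Both arms | 0.521 (+4%) | 0.544 (+9%) |
| Controls only | 0.495 (−1%) | 0.489 (−2%) |

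**5. Does imputation help?** A simulation used 2,500 trials, 60 per arm, r = 0.5, least-squares ANCOVA (the SAP plans a robust fit) and five imputed datasets. SAP 1.12 does not list the imputation model, so imputation from baseline FPG and arm was assumed. With DNA-arm removal only, the imputed estimates were 0.525 and 0.555, the same answer as complete cases. With everyone measured they were 0.498 and 0.500. Both-arm removal gave 0.520 and 0.545, and controls only gave 0.495 and 0.491.

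**6. If the diet has no effect.** When removal is unrelated to outcome there is no bias (simulated 0.000 and −0.002). When those removed from the DNA arm would have had higher week-6 FPG than those kept, the bias is the share removed times the gap: 10% × 0.3 = 0.03 up to 16.7% × 0.5 = 0.083 mmol/L in favour of the diet. The 16.7% is the whole loss allowance of Protocol 9.3 (10 of 60). In 4,000 simulated trials per setting (complete-case ANCOVA, no imputation), type I error rose to between 6.0% and 12.2%. With the same rate and gap in both arms the bias was about 0 and type I error 4.5% to 4.9%. With every discontinued participant measured it was 4.4% to 5.0%.

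**The case against.** The strongest reply is about reach. The no-tests sentence speaks of participant withdrawal, whereas the investigator's power is worded as discontinuing participation. The sentences after it, on an optional interview and no duty to give reasons, suit voluntary withdrawal. That narrower reading is possible. But the list just above mixes consent withdrawal and loss to follow-up with the investigator's grounds, no separate follow-up rule exists for discontinued participants, and ending someone's participation in the study would ordinarily end the visits too. If the narrower meaning is intended, the text still needs to say so.

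Second, the route is narrow. There is one scheduled contact between Day 0 and Day 42 in the two primary arms, no adherence threshold is defined for them, and nothing suggests that 3 to 6 people would be removed. Some who fail study requirements by missing visits would have no sample under any rule. This limits the likely size, and it stands.

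Third, SAP 1.12 imputes from the other variables, including outcomes, so Day-14 recall data could enter for those removed after Visit 5. The simulation used a simpler model, and a richer one was not tested. This stands as a limit on step 5, although one recall is a weak stand-in for adherence.

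Fourth, the shift is modest. The ANCOVA standard error is about 0.6 × √(1 − 0.25) × √(2/60) = 0.095 mmol/L, so 0.026 to 0.056 is roughly 0.3 to 0.6 of a standard error. The larger type I errors need one-sided removal at rates up to the full loss allowance. These points argue against alarm. They do not argue for keeping the rule.

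**Conclusion.** The concern holds and should be fixed. Followed as written, 4.5 can remove week-6 FPG selectively from an analysis that promises to include everyone randomised, and no planned analysis corrects for that. Under the illustrative assumptions the primary difference is overstated by about 5% to 11% when only DNA-arm non-compliers are removed. It is overstated by 4% to 9% when both arms are affected, and understated by 1% to 2% when only controls are. These figures rest on an assumed q, on no benefit over control in the DNA-arm participants removed and, where controls are removed, on zero change in them. The direction is not certain, and the bias is nil if the diet has no effect and those removed do not differ in outcome. The finding concerns investigator discontinuation only: ending tests after consent is withdrawn is correct, and stopping the advice does not by itself trigger removal.

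**What to change.** In Protocol 4.5, separate two events: stopping the assigned dietary advice, and withdrawing consent to further study measurements. State that non-compliance, protocol deviation or alternative treatment does not end clinic measurements, and that only withdrawal of consent or a recorded clinical reason such as pregnancy does. Limit the no-tests sentence to those cases. Invite everyone else to Visits 6, 8 and 10 as scheduled, with the Visit 6 fasting sample as the minimum. Bring 6.2.4 and 10.2 into line. Keep handling significant deviators through the per-protocol set, which already excludes them. As a supplement for those who still go missing, a delta-adjusted imputation analysis would show how far the result depends on missing at random.

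The cost is protocol wording, plus consent wording if the consent form or information sheet (not among the documents seen) repeats the rule. The visits and assays are already scheduled for every randomised participant, and the sample size does not change. The downsides are some effort to bring back people who have stopped the diet, and a possibly smaller observed effect.
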